11.9 Point of Enrollment

A consented patient will be registered into the study EDC (eCRFs) and a unique subject identification number at the time of registration will be issued via the EDC. All data will be entered in the study EDC. If a patient later declines to participate, or is excluded from enrollment, the investigator will note the reason for non-participation in the study EDC.

A patient is considered enrolled when the following milestones have occurred: (1) the ICF is signed, (2) all applicable screening has been successfully completed, and (3) all study inclusion criteria and no exclusion criteria are met. Since the final selection criteria are re-assessed prior to procedure initiation on the date

of treatment (e.g.: pregnancy test, current medications, active infections) the patient may not be enrolled until that date. Specifically, final eligibility must be confirmed by the investigator prior to initiating the Minitouch procedure.

For additional clarity, a consented patient that does not proceed to treatment for any reason (such as screen failure, declines treatment or participation), is categorized as consented-enrolled. A qualified patient in whom the Minitouch procedure is initiated is categorized as treated-enrolled.

11.10 Completion of the Clinical Investigation

The completion of the clinical investigation shall be the last visit of the last subject and when follow-up is complete for the clinical investigation, whether the clinical investigation concluded according to the protocol or was terminated prematurely.

12 STUDY VISIT INSTRUCTIONS

12.1 Schedule of Events

This section describes the timing for required testing and procedures during screening and in follow-up. All references to a study visit throughout the protocol are inclusive of visits conducted in person or via telemedicine visit (phone call, video, virtual office/remote), both of which are acceptable for purposes of trial conduct. The overall schedule of events is shown below. Results from these assessments will be captured in the patient's medical record or on source documents, and eCRFs. All study visit windows will be calculated based on the day of procedure (Day 0) and one month will be calculated as 30 calendar days, one week as 7 calendar days. **Section 13 STUDY PROCEDURES / EVALUATIONS** details the processes.

The study primary safety/efficacy endpoint assessment is conducted at the 12-month follow-up visit.

12.2 Validity Windows for Baseline Testing

All Baseline activities, including prescreening and rescreening testing must be conducted within the validity window. Review testing dates prior to procedure to ensure that all required activities have been conducted within window as outlined in **Table 12-1** below.

For example, the assessment of the patient's medical and surgical history must have occurred no more than 6 months prior to the date of treatment. If that assessment is outside of that validity window, then reassess the subject's medical and surgical history prior to the procedure.

| Table 12-1: Validity Windows | | |
|--|---|--|
| Screening Activity | Validity Window (where 6 months = 180 calendar days; and 12 months = 365 calendar days) | |
| Demographics | 6 Months | |
| Medical and surgical history | 6 Months | |
| Documented history of excessive menstrual bleeding | 6 Months | |
| Physical examination | 6 Months | |
| Pap-Smear | 12 Months | |
| Transvaginal ultrasound | 6 Months | |
| Endometrial biopsy | 12 Months | |
| Sonohysterography / hysteroscopy | 6 Months | |
| Complete Blood Count | 6 Months | |
| Serum FSH | 6 Months | |
| Urine Pregnancy Test | 6 Months | |

Page 32 of 65

CONFIDENTIAL & PROPRIETARY

| Table 12-1: Validity Windows | | | |
|--|--|--|--|
| Screening Activity | Validity Window (where 6 months = 180 calendar days; and 12 months = 365 calendar days) | | |
| Urine Dipstick Pregnancy Test (Day of Procedure) | 24 Hours | | |
| STD Tests | 6 Months | | |
| PBLAC | 6 Months* | | |
| Menorrhagia Impact Questionnaire | 6 Months | | |
| Dysmenorrhea-related pain | 6 Months | | |

* If the qualifying PBLAC diary was completed more than 3 months prior to the date of planned treatment, the investigator must verbally confirm with the subject that she continues to experience heavy menstrual bleeding, i.e., there has not been a clinically significant change in her menstrual status. It will be left to the investigator's judgment whether another monthly PBLAC diary is warranted to reconfirm eligibility prior to treatment.

12.3 Screening Visits

Before conducting any study-specific procedures, including modifications of medications, obtain written informed consent (See **Section 11.5, Informed Consent**) and register the patient in the EDC to obtain a unique patient identification number.

Site personnel may use their medical judgment to best organize patient eligibility testing in a way that optimizes data collection and minimizes invasive testing. Utilize the guidance in Sections 12.1 Schedule of Events and Section 12.2 Validity Windows for Baseline Testing.

The screening process may require more than one visit to accomplish all the screening requirements. Then final eligibility must be confirmed by the investigator prior to procedure initiation.

12.3.1 Suggested Order of Events:

- 1. Written informed consent
- 2. Determine if any SOC testing may be used
- 3. Demographic data
- 4. Medical and surgical history
- 5. Concomitant Medications / Treatments
- 6. Patient PBLAC training and testing
- 7. PBLAC diary and sanitary supply distribution (pads/etc.)
- 8. Urine pregnancy test (to rule out pregnancy prior to proceeding with invasive diagnostic testing)
- 9. Physical examination (to include height, weight and BMI)
- 10. Pap Smear
- 11. Endometrial biopsy
- 12. Ultrasound
- 13. Sonohysterography or hysteroscopy
- 14. Hematology/CBC
- 15. As needed, STD testing
- 16. Serum FSH
- 17. Menorrhagia Impact Questionnaire (MIQ)
- 18. Dysmenorrhea-related pain
- 19. If eligible, schedule procedure

12.3.2 Pictorial Blood Loss Assessment Chart

PBLAC data collection is the most important assessment in this study. It is the endpoint efficacy measure, it may be the most difficult criterion to meet with the requirement of a score of \geq 150, and its

administration may require more than one visit. Details on administrating PBLAC are provided in Section **13.11 PBLAC Diaries**.

12.3.3 Screen Failures

Candidates who sign an informed consent form and fail to meet the inclusion and/or exclusion `criteria or who terminate from the study prior to treatment initiation are defined as screen failures. Screen failures are excluded from participation in the study. In some cases, subjects may be rescreened (See **11.4 Rescreening**). If needed, obtain guidance from the Sponsor clinical staff to determine if a screen failed subject may be rescreened.

12.4 Procedure (Day 0) – Enrollment / Discharge

12.4.1 Procedure Visit Strategy

On the day of procedure, first complete the reassessment of the selection criteria. This will include urine pregnancy testing, vital signs, medication review, assessment for the presence of infection or STD. If the urine pregnancy test is positive, then the patient is a screen failure.

Ensure that all existing tests remain within the validity windows.

Once the final eligibility is confirmed, the patient is enrolled and may proceed to treatment.

Prior to administration of procedure meds, have the subject complete the pelvic pain NRS prior to the procedure as a baseline. Then the pelvic pain NRS will be assessed again at discharge and as part of the SOC 24-hour follow-up phone contact.

Perform the procedure using the anesthesia of choice (as appropriate) and in accordance with the IFU.

After the procedure, assess the patient for AEs, SAEs and UADEs, confirm/verify the patient's understanding of the PBLAC diary completion instructions (retrain if necessary) and issue PBLAC diary and sanitary supplies.

Schedule the SOC 24-hour follow-up phone contact and Week 2 post-treatment follow-up visit prior to discharging the subject.

12.4.2 Suggested Order of Events

- 1. Review eligibility criteria
- 2. Vital signs
- 3. Baseline pelvic pain NRS
- 4. Urine pregnancy test
- 5. Anesthesia
- 6. Minitouch treatment
- 7. Post-procedure pelvic pain NRS at discharge
- 8. Assess adverse events
- 9. Confirm Patient's understanding of PBLAC completion, re-train if necessary (prior to discharge)
- 10. PBLAC diary distribution and sanitary supplies (prior to discharge)
- 11. Schedule the SOC 24-hour follow-up contact and Week 2 post-treatment follow-up visit

12.5 Standard of Care Contact After 24 hours

Per standard of care procedures, the patient is to be contacted at the standard of care 24 hour (18-48 hours) post-procedure. The following will be assessed:

1. Procedure-related Pelvic Pain NRS

Page 34 of 65

CONFIDENTIAL & PROPRIETARY

- 2. Concomitant Medications/treatments
- 3. Assessment of adverse events

12.6 Week 2 Visit (± 7 days)

Ensure that the visit is conducted within the visit windows. The patient will not be expected to provide a PBLAC diary. If a patient cannot attend a visit within window, then collect as much information as possible within window via phone, letter or email.

12.7 Follow-up Visits Conducted 3 and 6 Months (± 2 weeks) After Treatment

At these study visits, the patient will bring in her monthly PBLAC diaries. Review all of the diaries during the visit to ensure that the diaries are being completed correctly. Retrain the patient if necessary.

Ensure that the visit is conducted within the visit windows. If a patient cannot attend a visit within window, then collect as much information as possible within window via phone, letter or email.

12.8 Endpoint Visit at Month 12 (± 4 weeks)

This is the endpoint visit. Ensure that the visit is conducted within window and if a patient cannot attend a visit within window, then collect as much information as possible within window via phone, letter or email. Specifically, try to obtain the 12 Month PBLAC diary within window for all patients.

12.9 Durability Visits Conducted 24 and 36 Months (± 8 weeks) After Treatment

The 24 and 36-month visit may be conducted via phone, letter, email or in person as described in Section 12.1.

The 36-month visit is the final study visit. Complete both the 36-Month Visit and the Study Completion eCRFs.

12.10 Pre-Endpoint Termination Visit

If a patient terminates from the study prior to the 12-month endpoint visit, collect as much as possible of the testing below.

- 1. Serious Adverse Event collection
- 2. Concomitant Medications / Treatments
- 3. PBLAC diary collection
- 4. Menorrhagia Impact Questionnaire (MIQ)
- 5. Dysmenorrhea-related pain (NRS)
- 6. Patient Global Evaluation
- 7. Investigator Global Evaluation
- 8. Assessment of Adverse Events / Serious Adverse Events

12.11 Unscheduled Visits

Collect source documentation from unscheduled visits as required to support the assessment of AEs, SAEs and UADEs. Record these events in the appropriate upcoming eCRF visit module.

Page 35 of 65

13 STUDY PROCEDURES / EVALUATIONS

13.1 Prescreening

Since this is standard of care information, varying information may be available. Therefore, review existing testing to see if any may fit within the validity windows.

The following clinical information to review for eligibility in prescreening is a suggestion only. Look for:

- Female patient age 30 to 50 years, inclusive
- Excessive menstrual bleeding due to benign causes
- o Ability to provide written informed consent

Eliminate candidates with any of the following (not an inclusive list):

- Pregnant
- o Known/suspected uterine cancer or pre-malignant conditions of the endometrium
- o Clinically significant or suspected adenomyosis
- Known clotting defects, bleeding disorders or conditions that would affect menstrual bleeding or menses in general
- Currently on medications that could thin the myometrial muscle, such as long-term steroid use (inhaler or nasal therapy for asthma or other pulmonary conditions are allowed)
- Currently on anticoagulants
- Previous medical/surgical treatments, or has other conditions, that could lead to anatomic/pathologic weakness or thinning of the myometrium (Classical caesarean section and transmural myomectomy are examples of such treatments that may interrupt the integrity of the uterine wall)
- Any general health condition which, in the opinion of the investigator, could represent an increased risk for the patient or limit the ability of the patient to complete study requirements.

13.2 Demographic Data and Medical History

Demographics are to be collected on all patients during screening, including age (based on day of consent), sex, race, and ethnicity. Height in centimeters (cm), body weight (kg, in indoor clothing but without shoes) and BMI will also be measured. BMI shall be calculated as kg/m2. The site should use the NIH website BMI calculator https://www.nhlbi.nih.gov/health/educational/lose_wt/BMI/bmi-m.htm. Alternatively, BMI can be calculated in EDC so long as height (cm) and weight (kg) are entered accordingly. Relevant specific medical history and current medical conditions will be captured.

Collect relevant medical diagnoses, specific medical history, surgical history and current medical conditions. In order to qualify, patients must have documented history or diagnosis of HMB, and therefore, source documents from non-participating institutions may need to be requested. History may also include failed or contraindication to medical therapy, subject-reported historical use of sanitary products consistent with HMB, menstrual cycles that interfere with normal daily activities (e.g., work, social/leisure) due to prolonged duration or heavy menstrual flow, date of subject's first perception of or when treatment was first sought for HMB, or assigned diagnosis code(s) consistent with HMB.

Other eligibility criteria potentially identified from medical history (not an inclusive list):

- Untreated/unevaluated cervical dysplasia, except cervical intraepithelial neoplasia I (CIN I)
- Previous endometrial ablation procedure
- Known/suspected abnormal uterine/pelvic anatomy or condition, such as frozen pelvis

Page 36 of 65

CONFIDENTIAL & PROPRIETARY

- Previous medical/surgical treatments, or has other conditions, that could lead to anatomic/pathologic weakness or thinning of the myometrium (Classical caesarean section and transmural myomectomy are examples of such treatments that may interrupt the integrity of the uterine wall)
- Known clotting defects or bleeding disorders
- Abdominal pelvic or gynecological malignancy

13.3 Physical Examination / Gynecological Exam

A physical exam will be performed according to the Schedule of Events (at Screening/Baseline), as well as when judged necessary by the investigator or designee. Physical exam will be conducted per SOC (pelvic exam) and will include a Pap smear (at baseline only). During the screening physical exam, consider the following criterion to detect clinically significant findings which are exclusionary:

Any general health condition which, in the opinion of the investigator, could represent an increased risk for the patient or affect the effectiveness of GEA treatment, or limit the ability of the patient to fully participate in the study.

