10 STUDY DESIGN

This study is a prospective, multi-center, open-label, single-arm, clinical investigation to evaluate the Minitouch Endometrial Ablation System in up to 126 premenopausal women with menorrhagia. The treatment procedure may be performed in an office setting or ambulatory / outpatient surgery centers/operating room (OR).

Candidates will be identified via review of existing patient records and, if necessary, as a result of IRBapproved recruitment advertisements (see **Figure 10-1: Study Execution Diagram**). Study staff will confirm general eligibility and identify already existing SOC (standard of care) testing which may be applied to the trial.

Study staff will obtain written informed consent as outlined in Section 11.5 Informed Consent.

Screening may require more than one visit. The first visit requires documentation of written informed consent and it is recommended that the visit include patient training on the method of collecting PBLAC diary data, a validated patient self-reported menstrual diary scoring system. ⁽²⁾

A subsequent visit may occur after approximately one month, and after completion of the PBLAC diary. The subject will return the completed PBLAC diary and the site personnel will confirm menorrhagia with a PBLAC a score of \geq 150. Then the patient will continue screening for additional eligibility assessments as outlined in **Figure 10-1: Study Execution Diagram** and **Section 12.3 Screening Visits.**

Patient enrollment occurs on the day of the treatment following confirmation of eligibility. Once confirmed, then the patient may undergo the Minitouch procedure. One day after procedure, the study staff will contact the patient to assess the patient's procedure-related pelvic pain level utilizing the NRS (0-10 scale). Every effort should be made to ensure the 24-hour contact is conducted even if the window falls on a weekend. The follow-up visits will occur at 2 weeks, 3 months, 6 months and 12 months, 24 months, and 36 months post-procedure. Total study duration for a Patient is approximately 37 months, including one month of pre-enrollment assessment, and 36 months post-treatment follow up.

CONFIDENTIAL & PROPRIETARY

***NOTE:** Final eligibility must be confirmed by the investigator prior to procedure initiation.

Figure 10-1: Study Execution Diagram

Page 26 of 65

CONFIDENTIAL & PROPRIETARY

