11.3 Patient Selection Criteria

Patients who meet the inclusion criteria and do not fulfill any of the exclusion criteria will be eligible for participation in this study.

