11.3.2 Exclusion Criteria

Patients will be excluded from this study if they meet any of the following criteria:

Patient Conditions:

- 1) Pregnant, or desires to retain fertility
- 2) Current or documented history of endometrial hyperplasia
- 3) Active endometritis
- 4) Clinically significant or suspected adenomyosis indicated by patient complaints, imaging or clinician's judgment
- 5) Active infection of the genitals, vagina, cervix, uterus, adnexa or urinary tract
- 6) Active pelvic inflammatory disease
- 7) Currently using an intrauterine device (IUD), including Mirena[™] device, and unwilling to remove the IUD
- 8) Presence of an implantable contraceptive device (e.g., Essure[®]) protruding into the uterine cavity
- 9) Active sexually transmitted disease (STD) at the time of ablation
- 10) Presence of bacteremia, sepsis, or other active systemic infection
- 11) Currently on anticoagulants
- 12) Known clotting defects or bleeding disorders
- 13) Currently on medications that could thin the myometrial muscle, such as long-term steroid use (except inhaler or nasal therapy for asthma or other pulmonary conditions)
- 14) Previous medical/surgical treatments, or has other conditions, that could lead to anatomic/pathologic weakness or thinning of the myometrium (Classical caesarean section and transmural myomectomy are examples of such treatments that may interrupt the integrity of the uterine wall)
- 15) Any general health, mental health or social situation which, in the opinion of the investigator, could represent an increased risk for the patient, or the ability of the patient to complete study requirements.

Patient Anatomy:

- 16) Known/suspected abnormal uterine/pelvic anatomy or condition, such as frozen pelvis
- 17) Abdominal, pelvic or gynecological malignancy
- 18) Untreated/unevaluated cervical dysplasia, except cervical intraepithelial neoplasia I (CIN I)
- 19) Previous endometrial ablation procedure
- 20) Abnormal or obstructed, or perforated cavity as determined by investigator via standard clinical practices (e.g., hysteroscopy, saline infusion sonohysterography). This includes, but is not limited to:
 - a. Septate or bicornuate uterus, arcuate uterus or other congenital malformation of the uterine cavity
 - b. Pedunculated or submucosal myomas distorting the uterine cavity or not fully resected
 - c. Polyps larger than 1 cm
- 21) Intramural or subserosal myomas > 3 cm in size, or any myoma that distorts the uterine cavity

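### Section 13.3 adds predicted poor effectiveness as an investigator-judged ground for exclusion that the exclusion list does not contain, in a single-arm trial tested against a fixed 66%

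*Combined protocol and SAP*

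**What the plan says.** Section 13.3 describes the screening physical examination and tells sites to "consider the following criterion to detect clinically significant findings which are exclusionary". The criterion concerns a general health condition judged by the investigator. One of its grounds is that the condition "could represent an increased risk for the patient or affect the effectiveness of GEA treatment".

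The matching item in the exclusion list is criterion 15 (Section 11.3.2, repeated in the synopsis). It covers a situation that "could represent an increased risk for the patient, or the ability of the patient to complete study requirements", and effectiveness is not mentioned. The prescreening list in 13.1 has its own version, for a condition that "could represent an increased risk for the patient or limit the ability of the patient to complete study requirements", again without effectiveness.

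Section 11.3 sets the eligibility rule: "Patients who meet the inclusion criteria and do not fulfill any of the exclusion criteria will be eligible for participation in this study".

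Section 10 states the design: "This study is a prospective, multi-center, open-label, single-arm, clinical investigation". Section 17.2 tests the success rate against the 66% OPC with an exact binomial test. Section 17.1.1 limits the ITT cohort to eligible women in whom the procedure was started. Section 12.3.3 keeps screen failures out of the study. Section 11.9 has the reason for non-participation of consented women entered in the EDC.

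**The concern.** A woman can satisfy every criterion in 11.3.1 and 11.3.2 and still be turned away under 13.3 because the investigator expects the treatment to work less well in her. That is selection on predicted outcome, with no objective threshold.

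In a randomised trial such a clause would act on both arms alike. Here there is one arm and a fixed external benchmark, so any successful prediction raises the tested rate without any change in the device. The women removed belong to no cohort: ITT requires that the procedure was started, and the per-protocol cohort is a subset of ITT. The planned safeguards (missing counted as failure, multiple imputation, tipping point) deal with missing outcomes among treated women and cannot reach women who were never treated. No tabulation of exclusions by reason is planned.

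**Working it through.** **Comparison of the passages**

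| Place | Patient risk | Ability to complete or take part | Predicted effectiveness |
|---|---|---|---|
| Synopsis, exclusion 15 | yes | yes | no |
| 11.3.2, exclusion 15 | yes | yes | no |
| 13.1 | yes | yes | no |
| 13.3 | yes | yes | **yes** |

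Section 13.3 is the only one of the four with the third ground. None of the 22 exclusions contains a general effectiveness ground. Adenomyosis, cavity abnormality and myomas may bear on effectiveness, but they are named conditions.

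**The plan's own sample size.** Inputs from 17.2.1: p0 = 0.66, p1 = 0.78, one-sided alpha 0.025, power 80%, Z test with null variance.

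n = [(1.960 × √(0.66 × 0.34) + 0.842 × √(0.78 × 0.22)) / 0.12]² = 113.26, rounded up to 114. This matches the plan. Adding 10% gives 114 × 1.1 = 125.4, so 126, as stated. (Dividing by 0.9 would give 127; the difference does not matter here.)

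**Decision rule.** For the exact binomial test at N = 126, the smallest c with P(X ≥ c | 126, 0.66) ≤ 0.025 is 94 successes (74.6%). Its actual size is 0.0239.

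**Illustration of selection.** The documents give no frequency of use for the clause and no success rate for the women it would remove. Both are assumed. Let f be the share of listed-eligible women excluded only on the effectiveness ground, and s the success rate they would have had. The true rate among all listed-eligible women is set at 66%, scored as the primary analysis scores it. The rate among treated women is then

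(0.66 − f × s) / (1 − f)

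and the chance of passing is P(X ≥ 94 | 126, that rate). For example, f = 5% and s = 30% gives (0.66 − 0.015) / 0.95 = 0.679.

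| f | s | Rate among treated | Chance of passing |
|---|---|---|---|
| none | – | 66.0% | 2.4% |
| 2% | 50% | 66.3% | 2.9% |
| 2% | 30% | 66.7% | 3.5% |
| 5% | 50% | 66.8% | 3.7% |
| 5% | 30% | 67.9% | 6.2% |
| 10% | 50% | 67.8% | 5.9% |
| 10% | 30% | 70.0% | 15.1% |
| any | 66% | 66.0% | 2.4% |

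The last row is the case in which excluded women do no worse than others; there is no inflation. If the true rate is 64%, excluding 10% with s of 30-50% raises the chance of passing from 0.7% to 1.9-5.9%.

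**The case against.** The strongest reply is that 13.3 is only a loose restatement of exclusion 15. It asks sites to consider the criterion, it is confined to clinically significant general health findings at a physical examination, and enrolment is governed by 11.3, 11.9 and the final eligibility check in the schedule of events. On that reading the extra words are a drafting slip. This may be so, but the text adds a ground and calls such findings exclusionary, so a site following it literally would depart from 11.3. If no new ground was intended, aligning the wording loses nothing.

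Several further points stand in part:

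- Exclusion 15 is itself open to judgement, so discretion remains after the fix. It is, however, discretion about risk and completion, not about expected outcome.
- The FDA letter quoted in Section 6 says the benchmark trials also screened for cavity distortions and lesions that could interfere with treatment. It also reports no significant effect of age, baseline PBLAC, uterine sound or fibroids. This weakens the idea that failures are easy to predict, but it does not address general health conditions. The quoted text does not show whether those trials had an open clause of this kind.
- Section 11.7.2 requires careful tracking of eligibility, and 11.9 records reasons for consented women. Such exclusions are largely traceable; what is missing is a plan to report them.

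A reader might also take 13.1 as a second added rule, because its reference to "conditions that would affect menstrual bleeding or menses in general" is wider than exclusion 12 ("Known clotting defects or bleeding disorders"). The documents do not support that. Section 13.1 presents its review items as suggestions only and its list as incomplete, so it is a prescreening aid and not an eligibility rule.

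**Conclusion.** The contradiction between 13.3 on one side and 11.3, exclusion 15 and 13.1 on the other is plain on the text. In this design the clause as written permits selection on predicted outcome, and no planned analysis could detect or undo it.

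The size of any bias is unknown. The figures of 2.9-3.5%, 3.7-6.2% and 5.9-15.1% for 2%, 5% and 10% excluded rest wholly on the assumed frequency, an assumed 30-50% success rate in excluded women, and a true rate exactly at 66%. The 15.1% is the upper corner of that range, not an estimate.

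A reader might infer three stronger things that the documents do not support:

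- That investigators may exclude any woman they expect to fail. Section 13.3 is limited to clinically significant general health findings.
- That expected failures have in fact been removed. Nothing shows how often the clause was used.
- That the treated women are a more favourable group than those behind the OPC. The quoted letter does not give enough detail to compare them.

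**What to change.** - Reconcile 13.3 with exclusion 15 so that predicted effectiveness is not a separate, open-ended ground for exclusion. If the sponsor wants particular conditions excluded, they belong by name in 11.3.2; which conditions is a clinical question outside this review.
- State in 13.3 that only 11.3.1 and 11.3.2 determine eligibility.
- Report beside the primary result the number of consented women screened out on the effectiveness ground, using the reasons already entered in the EDC. Women turned away before consent may have no EDC record, so the count may cover consented women only.
- Optionally, align the bleeding-conditions wording in 13.1 with exclusion 12 for consistency.

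The cost is a minor amendment with the approvals and training described in 21.4: sponsor, FDA as appropriate, and IRB. The sample size stays at 114 evaluable and 126 enrolled, and no visits are added. The treated population may become slightly less favourable, which the listed criteria already allow.
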